A project led by the
European Foundation for the Care of Newborn Infants (EFCNI)

**Hospital self-assessment tool
for the implementation of the
European Standards of Care for Newborn Health
(ESCNH)**

european standards of
care for newborn health

Brief Title:
Self-assessment tool for implementing the ESCNH

—

Study Protocol and statistical analysis plan

Background

Uniform reference standards for the optimal care of preterm and ill newborns were developed and published in 2018 by the European Foundation for the Care of Newborn Infants (EFCNI) and a transdisciplinary network (1).

The so-called European Standards of Care for Newborn Health (ESCNH) cover a broad range of topics associated with preterm birth and neonatal mortality and morbidity. These 102 evidence-based standards are not legally binding but should be considered as guidance to develop binding country-specific guidelines, regulations or laws (1).

Alongside the continuous update and development of new standards, several initiatives across Europe were undertaken to implement the ESCNH in the hospital setting. However, it remains a challenge for care providers to identify the most important areas to efficiently change established procedures or to evaluate the extent to which the ESCNH are pursued. Therefore, we are aiming to develop a self-assessment tool in different languages helping care providers across Europe to measure the level of implementation of the ESCNH, to pinpoint possible inhibitors and to identify areas of a successful implementation.

With the goal to develop the ESCNH self-assessment tool, we advance the implementation of the ESCNH and pursue the mission to ensure harmonised, high-quality treatment and care throughout Europe in order to reduce care- and health-related inequalities for newborn infants and their parents and families.

Aim

We are aiming to develop a uniformly applicable self-assessment tool in different languages with the overall goal to support care providers across Europe to measure the level of implementation of the ESCNH recommendations, to pinpoint possible inhibitors, to demonstrate areas of a successful implementation, and ultimately to increase the extent of implementation and thereby reduce variation in care practices.

Study design and methods

eDelphi surveys and workshop

Covering the broad variety of the 102 standards in one hands-on and easy-to-use self-assessment tool requires their abbreviation and careful prioritisation. By means of qualitative research, we aim to approach this in a systematic and scientific manner using the eDelphi method to condense and prioritise the ESCNH into one questionnaire, the preliminary framework of the self-assessment tool. For this purpose, we will conduct a two-stage, electronic (e)Delphi survey followed by an expert workshop among invited healthcare professionals from various related disciplines as well as parent representatives.

The study preparation includes planning meetings with the Project Expert Group (PEG) consisting of 8 renowned experts and EFCNI members to define the methodological approach, the project timeline and to support and monitor of the development process of the eDelphi

survey. Within 4-5 meetings with the PEG, the first template for the eDelphi questionnaire will be developed and refined.

In the first eDelphi round, a group of approximately 100 healthcare professionals and parent representatives (see **Inclusion criteria** and **Exclusion criteria**) - the eDelphi panel - is invited to fill out the eDelphi questionnaire. The panel will receive an access-link to the online questionnaire, created using SurveyMonkey software, which will be completed anonymously. Next to participant-related information such as expertise or country of location, the questionnaire will cover specific aspects of the eleven major topics of the ESCNH. In addition, the questionnaire entails evaluation questions asking for the appropriateness of the wording and the completeness of the questionnaire with regards to the ESCNH content. In a subsequent eDelphi round, the panel will receive an updated questionnaire showing the aggregated results of the first eDelphi round. Thus, panellists will have the chance to re-assess the questionnaire based on the added quantitative and qualitative information provided by the responses of other participants. This will help to build consensus among disparate stakeholder groups. The final step of the eDelphi procedure is a digital expert workshop with 15–20 panellists preselected with regards to their respective expertise and country representation. In this workshop remaining disagreements will be discussed until consensus is reached. The final agreed-upon questionnaire will constitute the first version of the self-assessment tool, which will then be piloted.

Pilot-testing

The pilot-testing will be carried out in diverse real-life settings (n = min 10 hospitals) in Germany, UK, France, Italy, Sweden, Portugal, and Spain. Cooperating hospitals will receive online access to the self-assessment tool to appraise the implementation of the ESCNH in their hospital. Participants of the pilot study will have the option to appraise the self-assessment tool via an adjacent evaluation form. Both, the self-assessment tool and the evaluation form will be made available in the respective language via online questionnaires in SurveyMonkey. The pilot-testing will assess the user-friendliness of the self-assessment tool (duration of completion, illustration on screen, understandability) and also gather feedback on the applicability of selected ESCNH content, the formulation of statements, illustration of output and the utilisation of the self-assessment tool. Based on the results of the pilot-testing, the self-assessment tool will be updated and subsequently published.

Study population

The PEG consists of 8 renowned experts of multidisciplinary professions: neonatologists, neonatal nurses, midwives, obstetricians, parent representatives, health sociologists and a statistician and is completed by EFCNI members.

The *eDelphi panels* will consist of experts from various European countries from the following fields: neonatology, midwifery, (neonatal) nursing care, obstetrics, parent representing institutions, psychology, health sociology and physiotherapy.

Participants for the *pilot-testing* will be hospital staff with varying professional background, depending on the respective target groups which will be derived from the *eDelphi* questionnaires.

Inclusion criteria

Participants will be eligible if they are

- parent representatives or representatives of caregivers of infants who received special/intensive care,
- healthcare professionals in the field of neonatology, midwifery, neonatal nursing care, obstetrics, psychology, health sociology, physical therapy, or
- hospital management.

Exclusion criteria

Participants will be excluded if they

- provide insufficient proficiency of English for the *eDelphi* questionnaires or the languages of the self-assessment tool in the pilot testing, or
- have a professional background that is not related to the ESCNH / individuals that are not parent representatives or representatives of caregiver of infants who received special/intensive care.
- primarily work in the industry.

Sample size

To gain meaningful descriptive data, the *eDelphi* panel is aimed at about 100 participants with a minimum size of 50 participants. For pilot-testing a minimum of 10 participating neonatal intensive care units is targeted.

Recruitment of study participants

EFCNI's European network of parent organisations and healthcare professional societies of more than 220 institutions as well as supporters of the ESCNH project including, next to organisations, also authors, co-authors, and chair committee members of the ESCNH, will be approached via mail and invited to participate in the *eDelphi*. In addition, members of the PEG will share information on participation in the *eDelphi* within their network and will provide support in the identification of respective hospitals for the pilot-testing. The recruitment will take place over the European associations of the respective healthcare professionals as well as through targeted invitations in order to reach a representative panel size and mix.

Study outcomes

Primary outcome measures

- Online self-assessment tool (including statements and questions)

Secondary outcome measures

- Response rates
- Demographics and characteristics
- User-friendliness score of the self-assessment tool (time taken to fill in, illustration on screen, understandability)
- Applicability score of selected ESCNH content
- Applicability score of the formulation of the questions
- Qualitative feedback on illustration of output
- Appraisal on the utilisation of the self-assessment tool
- Scalability of the self-assessment tool and dissemination

Statistical analyses

The analyses will include descriptive statistics such as frequencies with percentages, mean and variance (metric scaling, variables with approximately symmetrical distribution), median and interquartile range (ordinal scaling as well as metric scaling for clearly skewed distributed variables). Tabular and graphical mapping of response rates for the pilot-testing including error margins plotted and broken down by type of healthcare facility and geographical region. Analyses will be performed with MS Excel and (if needed) R Studio.

Informed consent and data collection

Prior to the study participation, interested individuals will be informed about the following points:

- background and relevance of the study,
- type and form of data collection (anonymous) and data usage,
- the General Data Protection Regulation (GDPR), voluntariness of participation,

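### Does the pilot response rate need a fuller definition before it can be reported with error margins?

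*Combined protocol and SAP*

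**What the plan says.** Study outcomes lists response rates among the secondary outcomes, without a definition. Statistical analyses adds only the presentation for the pilot: "response rates for the pilot-testing including error margins plotted and broken down by type of healthcare facility and geographical region". The rest of that section is descriptive and includes counts with percentages. It names no interval method or confidence level.

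Pilot-testing describes two forms. The first is the tool: "Cooperating hospitals will receive online access to the self-assessment tool to appraise the implementation of the ESCNH in their hospital". The second is optional: "Participants of the pilot study will have the option to appraise the self-assessment tool via an adjacent evaluation form". The same section then says: "Based on the results of the pilot-testing, the self-assessment tool will be updated and subsequently published".

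The pilot's size and participants are described in three ways:

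- Pilot-testing: "diverse real-life settings (n = min 10 hospitals) in Germany, UK, France, Italy, Sweden, Portugal, and Spain".
- Sample size: "For pilot-testing a minimum of 10 participating neonatal intensive care units is targeted".
- Study population, on the pilot participants: they "will be hospital staff with varying professional background".

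Recruitment of study participants says that members of the expert group "will provide support in the identification of respective hospitals for the pilot-testing". The number of hospitals to be approached and the number of staff per hospital are not given.

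**The concern.** A rate needs a numerator, a unit and a denominator, and a plotted margin needs a method. Here all four are open. The choice of form looks the most serious. The appraisal of the tool is collected on the optional form, so tool completion could be full while few people supplied the opinions that guide the revision. A single rate based on the tool would not show this. If a participating site were taken to mean one that completed the tool, the rate among participating sites would be 100% whatever happened.

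The unit could be the hospital, the neonatal intensive care unit or the staff member. With about 10 sites split by facility type and region, the interval method could also decide what the graph shows. At stake is whether a reader can tell how far the user-friendliness and applicability results rest on those who chose to answer.

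**Working it through.** **Inputs.** From the plan: a minimum of 10 sites, seven named countries and two forms. Assumed, because the documents give no figures: 20 hospitals approached (range 15–30), 10 taking part and all completing the tool, 6 evaluation forms returned (range 3–8), 95% confidence. The plan states no response rate or precision, so there is no figure to reproduce.

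**1. Numerator and denominator.** The exact interval for x of n runs from the 0.025 quantile of Beta(x, n−x+1) to the 0.975 quantile of Beta(x+1, n−x). When x = n the upper limit is 100%; for 10/10 the lower limit is 0.025^(1/10) = 69.2%.

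| Rate | k/n | % | Exact 95% interval |
|---|---|---|---|
| Tool, of sites taking part | 10/10 | 100 | 69.2–100 |
| Form, of sites taking part | 6/10 | 60 | 26.2–87.8 |
| Tool, of sites approached | 10/20 | 50 | 27.2–72.8 |
| Form, of sites approached | 6/20 | 30 | 11.9–54.3 |

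Over the assumed ranges, tool completion among sites approached runs from 10/30 = 33.3% (17.3–52.8) to 10/15 = 66.7% (38.4–88.2). Form return among sites taking part runs from 3/10 = 30% (6.7–65.2) to 8/10 = 80% (44.4–97.5).

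The spread is wide, but these are four different quantities, not rival estimates of one. Once the count is printed with its percentage, the reader can see the base. The number of forms returned would also be visible as the number behind the user-friendliness and applicability scores.

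**2. Interval method at n = 10.**

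| k/n | Normal approximation | Wilson | Exact |
|---|---|---|---|
| 8/10 | 55.2–104.8 | 49.0–94.3 | 44.4–97.5 |
| 10/10 | zero width | 72.2–100 | 69.2–100 |

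The normal approximation, p ± 1.96√(p(1−p)/n), behaves badly here, but the plan does not name it. Wilson and exact intervals lead to the same reading: the rate is imprecise.

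**3. Single-hospital countries.** With 10 hospitals and at least one in each of seven countries, 10 − 7 = 3 are left over. At most 3 countries then have two or more, and at least 7 − 3 = 4 have exactly one. For 1/1 the normal-approximation margin is zero, Wilson gives 20.7–100% and exact gives 2.5–100%. This needs exactly 10 hospitals (10 is a floor), all seven countries contributing, the hospital as unit, and region meaning country. The plan speaks of geographical region. With two regions of five hospitals such cells do not arise, though 3/5 still has an exact interval of 14.7–94.7%.

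**4. Clustering.** The design effect is 1 + (m − 1)×ICC for m staff per hospital. With m = 1 it is 1.0 at any ICC. With 10 hospitals, m = 5 and a rate of 80%, the half-width is 1.96√(0.8×0.2/50) = 11.1 points if clustering is ignored. At ICC 0.3 the design effect is 1 + 4×0.3 = 2.2 and the half-width 1.96√(0.8×0.2×2.2/50) = 16.4 points. At m = 20 and ICC 0.3 the design effect is 6.7, which widens margins by a factor of √6.7 = 2.59. Neither m nor the ICC is in the documents, and the matter arises only if staff are the unit and the rate is generalised beyond the pilot hospitals. The plan says neither.

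**5. Unit and base, from the text.** Access goes to hospitals so that they can appraise themselves, both size floors count sites, and one breakdown is by facility type. These point to the site as the unit, without settling it, since staff could also be classified by facility. Sites given access are the natural base, and that base does not force 100%. Hospital against neonatal intensive care unit is a difference of wording that hardly alters a rate if each hospital contributes one unit.

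**6. What the rate feeds.** The primary outcome is the tool. No test, threshold or stop/go rule uses the response rate, and the revision draws on the pilot feedback.

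**The case for a change.** The strongest case for a change is that this outcome is the only one given its own sentence of planned presentation, in a document that calls itself a statistical analysis plan, so asking how it will be calculated is fair. A larger pilot would not settle which form, unit or base is meant. Timing matters too: Informed consent and data collection says that data are collected anonymously, and no log of sites approached or links sent is described, so that base may be hard to recover afterwards.

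The factual core stands: none of the four elements is defined anywhere, and the site is named in two ways. The timing point has force only if sites approached are chosen as the base, which the plan does not promise; sites given access must be known to whoever issues the access. The argument that a tool-based rate would hide non-response on the optional form assumes that an analyst with two forms and a commitment to counts would report one form and suppress the other. Nothing in the plan leads there.

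**Conclusion.** No change to the plan is called for. The gap is real but is one of detail. The plan states no wrong number and no rule that misleads when followed, and the usual practice of giving counts and percentages for each form, with a small-sample interval wherever margins are drawn, fills it. The spread from 30% to 100% depends on assumed counts of sites approached and forms returned. The zero-width margin depends on a method the plan does not name, and the clustering factor on staff numbers and an ICC it does not give. Whichever definition is used, a rate based on about 10 sites stays imprecise: 5/10 has a Wilson interval of 23.7–76.3%, so a fuller definition would clarify the label without improving the information. The conclusion assumes that the rate remains descriptive and that no decision is later tied to it.
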